### **13.3.2 Laboratory measures, vital signs, physical examination**

For clinical safety laboratory test results and vital signs, the numeric values and corresponding changes from baseline will be summarized using descriptive statistics by parameter and time point for the following parameters:

Hematology (Basophils, Basophils/Leukocytes, Eosinophils, Eosinophils/Leukocytes, Lymphocytes, Lymphocytes/Leukocytes, Monocytes, Monocytes/Leukocytes, Neutrophils, Neutrophils/Leukocytes, Platelets, Erythrocytes, Leukocytes)

Chemistry (Alkaline Phosphatase, Alanine Aminotransferase, Aspartate Aminotransferase, Bilirubin, Creatinine, Gamma Glutamyl Transferase, Urea Nitrogen)

Vital Signs (Systolic and diastolic blood pressure, Heart Rate, Body Temperature, Respiratory Rate.)

In addition to the tables showing the distribution parameters, laboratory measures will be presented in ‘shift tables’ that show the position of all patients relative to the applicable reference range at clinical trial entry, broken down by the position at V3 and at EoT.

---

For physical examination results, tables of frequencies will be prepared, broken down by treatment group and visit.

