9.2 Patient Exclusion Criteria

1. Other acute or chronic restrictive or obstructive lung diseases, including but not limited to: Patients with clinically active asthma (variable and recurring symptoms of airflow obstruction and bronchial hyper-responsiveness), chronic obstructive pulmonary disease, interstitial lung disease, or cryptogenic organizing pneumonia or other causes of restrictive lung disease such as neuromuscular weakness or diaphragmatic paralysis.
2. Any acute pulmonary bacterial, viral (as confirmed by multiplex PCR) or fungal infection not successfully resolved at least 4 weeks prior to the Screening Visit.
3. Chronic renal dysfunction with serum creatinine ≥ 2.5 mg/dL.
4. Chronic hepatic dysfunction with serum total bilirubin > 5 x upper limit of normal (ULN), transaminases > 5 x ULN, or alkaline phosphatase > 5 x ULN.
5. Evidence of clinical relapse of the primary malignancy, according to investigator's judgement, which warranted allogeneic bone marrow transplant.
6. Use of azithromycin within 4 weeks prior to Randomization (Visit 1).
7. Chronic oxygen use or use of non-invasive ventilation.
8. Active smokers (i.e. any kind of inhaled nicotine consumption).
9. Pregnant women or women who are unwilling to use appropriate birth control to avoid pregnancy over the course of the clinical trial (for details see [Appendix II](#)).
10. Women who are currently breastfeeding.
11. Known hypersensitivity to L-CsA or to cyclosporine A.
12. Patients with life-expectancy of less than 6 months.
13. Receipt of an investigational drug as part of a clinical trial within 4 weeks prior to the Screening Visit. Participation in registries, , is allowed

14. Psychiatric disorders or altered mental status precluding understanding of the informed consent process and/or completion of the necessary procedures.
15. Any co-existing medical condition that in the Investigator's judgment will substantially increase the risk associated with the patient's participation in the clinical trial.
16. Pre-scheduled hospitalizations, surgeries or interventions planned to be performed after obtaining Informed Consent for this study.

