In addition to the Investigator's own description of the AE, each AE event will be coded by data management according to the Medical Dictionary for Regulatory Activities (MedDRA) code list. The verbatim term will be recorded in the eCRF.

Abnormal laboratory test results will be reported as AEs if they are indicative of a clinical condition that meets the criteria for an AE.

Adverse Drug Reaction (ADR)

Adverse drug reactions (ADRs) are all noxious and unintended responses to a medicinal product related to any dose that a causal relationship between the medicinal product and an AE is at least a reasonable possibility, i.e., the relationship cannot be ruled out. An unexpected ADR is any adverse reaction not identified in nature, frequency, or intensity listed in the referent safety section of the current IB.

Serious Adverse Event (SAE)

Each AE is to be classified by the Investigator as SERIOUS or NON-SERIOUS.

The International Conference on Harmonisation (ICH) of Technical Requirements for Registration of Pharmaceuticals for Human Use defines an SAE as any AE occurring at any dose that results in any of the following outcomes:

- Death
- A life-threatening event (immediate risk of death at the time of the event)
- Inpatient hospitalization or prolongation of existing hospitalization
- A persistent or significant disability/incapacity
- A congenital anomaly/birth defect
- Other important medical event (Medical and scientific judgment should be exercised in deciding whether expedited reporting is appropriate in other situations, such as important medical events that may not be immediately life-threatening or result in death or hospitalization but may jeopardize the patient or may require intervention to prevent one of the other outcomes listed in the definition above. These should also usually be considered serious.)

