# 9 STATISTICAL CONSIDERATIONS

## 9.1 General Considerations and Descriptive Statistics

Analyses and outputs will be produced using SAS® software PPD, version 9.4 or later, or other suitable, commercially or publicly available statistical software, in a secure and validated environment. All tables, figures and data listings to be included in the report will be independently checked for consistency and integrity.

The data recorded in the eCRF will be summarized as appropriate, per treatment group and for the applicable total analysis population, using the following descriptive measures:

- All continuous assessments will be summarized using descriptive statistics (i.e., n, mean, standard deviation, median, Q1, Q3, minimum, and maximum).
- All categorical assessments will be summarized by using frequency counts and percentages.
- Discrete ordinal or higher-level data will be summarized as continuous data, but a tabulation of categories may also be included, depending on the number of categories.
- “Missing” category should be added for a categorical variable if there is at least one subject with missing data for that categorical variable unless the following evaluation requires otherwise.

For all measures analyzed, tabulations comparing the treatment groups will be prepared. For outcomes measured more than once, the analyses will include tabulations of the measured values

---

by visit, as well as change from baseline. Where provided, all confidence intervals will be two-sided 95% intervals.

All data recorded in the eCRF will be listed in subject data listings.

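### The laboratory shift tables cannot register worsening in patients who enter above range and skip Visits 2 and 4, and no planned laboratory table counts patients by size of worsening or by worst post-dose value

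*SAP*

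**What the plan says.** SAP 8.3 makes clinical laboratory values part of the primary endpoint (tolerability and safety in the first 4 weeks). SAP 14.1 repeats the analyses over the whole randomized treatment period as a secondary assessment.

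SAP 13.3.2 plans two laboratory outputs:

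- **By-visit summaries.** For each laboratory parameter, "the numeric values and corresponding changes from baseline will be summarized using descriptive statistics by parameter and time point". SAP 9.1 defines the statistics as "n, mean, standard deviation, median, Q1, Q3, minimum, and maximum".
- **Shift tables.** These show each patient's position "relative to the applicable reference range at clinical trial entry, broken down by the position at V3 and at EoT".

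SAP 9.1 adds that "All data recorded in the eCRF will be listed in subject data listings".

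On who may enter, Protocol 9.2 excludes "Chronic renal dysfunction with serum creatinine ≥ 2.5 mg/dL". It also excludes chronic hepatic dysfunction with total bilirubin, transaminases or alkaline phosphatase above 5 x ULN. Values below those limits are admissible under these criteria.

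The schedule of activities (Protocol 13, SAP Table 1) has laboratory tests at Screening and V1 to V6. V3, V4 and V6 may be remote because of COVID-19, and the remote column contains no laboratory test. Tests are run locally against each laboratory's own normal range (Protocol 12.1.6).

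Neither document plans graded categories, multiples of ULN or of baseline, or a worst post-baseline value.

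**The concern.** A shift table is the usual place to see how many patients moved in the wrong direction. Here it is also the only planned laboratory output that refers values to the reference range. Its top category is simply above range, and the entry limits let patients start there for exactly the kidney and liver parameters a reader will look at in a cyclosporine trial. A stable patient and a patient whose value triples fall in the same cell.

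The table also reads single visits. A rise at V2 or V4 that has settled by V3 or V5 produces no shift, even in a patient who started within range. If V3 is remote, that patient contributes nothing to the primary-window shift.

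At stake is the statement the clinical study report can make. A table with no upward shifts could be taken as evidence that no patient worsened, when for some patients it could not have shown otherwise. To find the number who worsened, a reader would have to count from listings with criteria chosen after the data are seen.

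**Working it through.** The plan states no figure on this point, and the sample size (3 x 8 = 24) rests on feasibility, so there is no planned number to reproduce. Three checks follow.

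**1. Ceiling of the shift table**

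Inputs: entry limits from Protocol 9.2. The creatinine ULN is not in the documents; I assume 1.0, 1.2 and 1.3 mg/dL. I read position relative to the range as below, within or above.

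Rule: if baseline b > ULN and the value is multiplied by f ≥ 1, then f x b > ULN. The category cannot change.

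| Parameter | Entry values | Rise | Later values | Combinations | Classed above to above |
|---|---|---|---|---|---|
| Creatinine (mg/dL) | 1.5, 2.0, 2.4 | 1.5-, 2-, 3-fold | 2.25 (1.5 x 1.5) to 7.2 (2.4 x 3) | 3 ULNs x 3 x 3 = 27 | 27 |
| Transaminase (x ULN) | 1.5, 3, 5 | 2-, 3-fold | 3 (1.5 x 2) to 15 (5 x 3) | 3 x 2 = 6 | 6 |

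The rule holds for any ULN below the baseline value, so the result does not depend on the assumed ULN.

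**2. Visits used**

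- On-treatment post-baseline laboratory visits: V2, V3, V4, V5 = 4. Used in shifts: V3 and V5 = 2 of 4.
- Primary window: V2 and V3 = 2. Used: V3 = 1 of 2.
- Primary window with a remote V3: one sample (V2) exists and none is used.

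**3. What the by-visit summaries show**

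Illustrative arm of 8 with baseline creatinine 0.8, 0.9, 0.9, 1.0, 1.0, 1.1, 1.6, 2.0 mg/dL (invented values).

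| At V2 | Mean change | Median change | Q3 of change | Maximum change |
|---|---|---|---|---|
| One patient rises 2.0 to 4.0 | 2.0/8 = 0.25 | 0 | 0 | 2.0 |
| A second also rises 1.6 to 3.2 | (2.0 + 1.6)/8 = 0.45 | 0 | 0.4 (linear interpolation) | 2.0 |

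The single peak is visible: the maximum value goes from 2.0 at baseline to 4.0 at V2, and the maximum change is +2.0. The second patient, whose value also doubled, leaves the maximum unchanged and shows only as a movement in the mean and Q3. In this tidy example, where everyone else changes by exactly zero, that movement could be traced back. With ordinary visit-to-visit scatter it does not convert into a count.

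Two further limits follow from the form of the summary:

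- A change in mg/dL is not a relative change. A rise of 0.8 is a doubling from 0.8 (1.6/0.8 = 2) but only 1.4-fold from 2.0 (2.8/2.0 = 1.4).
- Each visit has its own row. If the V2 and V4 rows both show a high maximum, the table does not say whether this is one patient or two.

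**The case against.** A reader might infer that worsening in patients with raised baselines is invisible, or that peaks at V2 and V4 never appear. The documents do not support that. The by-visit summaries cover every time point and include the maximum, as check 3 shows. The listings give every value for all 24 patients, and unscheduled measurements go into the eCRF as well (Protocol 13.2.6). With a remote V3, the V2 value still enters the primary by-visit summary; only the V3 shift is missing.

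Adverse event reporting is a further safeguard. Protocol 12.1.1 counts worsening of a pre-existing condition as an AE, SAP 10.3.1 counts such worsening as treatment-emergent, and Protocol 12.1.6 has the investigator check and interpret each result. The DMC also reviews safety under a separate SAP. Against this, the route from laboratory value to AE depends on judgement: "Abnormal laboratory test results will be reported as AEs if they are indicative of a clinical condition that meets the criteria for an AE". Only patients are blinded (Protocol 8.3.1), so that judgement may be made by someone who knows the arm.

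Three other inferences should be resisted:

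- The protocol does not state an expectation of no nephrotoxicity. Sections 6.1.3 and 6.1.4 describe data to date.
- The entry limits show who may enter, not how many will enter above range. The documents give no basis for estimating that share.
- Counting V6 as a missed visit overstates the loss. It is follow-up two weeks after treatment ends, outside the randomized treatment period that SAP 14.1 analyses.

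It is also fair to say that no planned inference changes, because the trial is descriptive, and that finely banded tables at 8 per arm will be sparse. What the objection leaves standing is the missing count: the maximum speaks for one patient per arm and visit, and listings are data rather than a pre-specified summary.

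**Conclusion.** The point holds in limited form. The shift tables have a ceiling for patients above range at entry, use 2 of 4 on-treatment laboratory visits, and can be empty for the primary window when V3 is remote. Worsening can still be found in the by-visit maxima and the listings. What is missing is any laboratory table that counts patients by size of worsening or by worst post-dose value, for a component of the primary safety endpoint.

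The ceiling rests on the SAP text and the entry limits alone. The practical size depends on how many patients enter above range and how many V3 visits are remote; neither is known from the documents. In a descriptive trial of 24 patients this is a minor to moderate reporting improvement, not a flaw that undermines the trial.

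**What to change.** In SAP 13.3.2, keep the existing tables and add, for key chemistry parameters:

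- **(a) Shift tables from baseline to the worst value after the first dose**, once for samples up to V3 and once up to EoT, using all scheduled and unscheduled samples. Place bilirubin, ALT, AST, GGT and ALP in pre-specified multiples-of-ULN bands (for example ≤1, >1-3, >3-5, >5-10, >10 x ULN), using the range of the local laboratory that ran the sample.
- **(b) A count table of patients by maximum creatinine ratio to own baseline** (for example <1.5, 1.5-<2, 2-<3, ≥3), for the same two periods. This cannot be a shift table, because every patient's baseline ratio is 1.

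Give as denominator the patients with at least one post-dose sample in the period. A patient with a remote V3 then still contributes through V2. The bands are reporting categories only and carry no clinical rule; the sponsor may choose others if they are fixed before unblinding.

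The cost is SAP wording and a few more tables from data already collected. The downside is more output, sparse cells at 8 per arm, and more abnormal values on show in every arm, placebo included.

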### **13.4 Analysis Population**

In this trial whose primary measures are safety and tolerability related outcomes, the applicable analysis population will be the SAF. See Sections 10.2.1 and 10.3 for further details.

### **13.5 Working Hypothesis**

Not applicable.

### **13.6 Analysis Model**

Not applicable.

### **13.7 Sensitivity Analyses for the Primary Endpoint**

Not applicable.

## **14 SECONDARY ASSESSMENTS**

### **14.1 Local and Overall Tolerability, and Safety**

In the context of secondary assessments i.e. IMP tolerability and safety during the first 12 weeks of treatment, all analyses described in Section 13 will be performed for the entire randomized treatment period.

For all tabulations broken down by visit, no separate tabulations for primary and secondary assessments are required as the results for the period up until Visit 3 are a subset of those for the entire period of observation and can thus be taken from the same table.

All analyses will be carried out in the SAF set.

### **14.2 CsA Pharmacokinetics**

PK analyses will be carried out using SAS® software, Version 9.4 or later. Descriptive statistics (N, arithmetic means, standard deviation, geometric means, geometric coefficient of variation, medians, minimum and maximum) will be presented for all PK parameters indicated in section 8.4 including Whole blood trough level parameter (Cyclosporine A Concentration) at Weeks 2, 4, 8, and 12, separately for each treatment group. A figure with overlaying individual pharmacokinetic concentration-time profiles will be presented for plasma concentrations after end of inhalation per treatment group.

---

The statistical analysis will be carried out on a log scale for  $AUC_{0-4\text{ h}}$  and  $C_{\max}$ -values, while  $t_{\max}$  and trough levels will be evaluated on a linear scale.

Analyses of variance will be performed to compare the treatment groups with regards to  $AUC_{0-4\text{ h}}$  and  $C_{\max}$ . This will include the computation of 95% confidence intervals for the between-group differences.

The statistical analysis will be performed as a valid case analysis including all patients of the FAS.

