Statistical Considerations:	
Exploratory statistical analyses will be performed using methods of descriptive data analysis.
 
Analysis of safety: MedDRA coded, treatment emergent adverse events (TEAEs) will be tabulated at the Preferred Term (PT) and the System Organ Class (SOC) levels. Treatment group comparisons of the proportion of patients with TEAEs will be based on Wilson score confidence intervals. Pairwise group comparisons will be provided at the SOC level as well as for the events identified as local tolerability measures (cough, wheezing, bronchospasms, throat irritation, change in FEV₁), with separate analyses for all events with onset during the first 4 weeks of treatment and for events with onset at any time during randomized treatment. CGI scales will be analysed and compared between the treatment groups.
 
Analysis of efficacy: Spirometric variables and SF-36 scales will be analyzed and compared between the treatment groups using mixed models for repeated measures (MMRM).
 
Pharmacokinetic measures: The statistical analysis will be carried out based on a multiplicative model for AUC_{0-4 h} and C_{max} values, while t_{max} and trough levels will be evaluated on the basis of an

	
additive model. Analyses of variance will be performed to compare the treatment groups.
 
Sample size determination: The sample size for the study was established based on considerations of feasibility rather than on power calculations. A total of 24 patients (3 arms x 8 patients each) are planned to be randomized.

--	---

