14.2.5 Pharmacokinetic Variables

The statistical analysis will be performed as a valid case analysis including all patients of the FAS. No subgroup analysis is planned.

Descriptive statistics will be used by the **CCI** (N, arithmetic means, standard deviation, geometric means, geometric coefficient of variation, medians, minimum and maximum) and will be presented for all PK parameters indicated in [Section 8.1.6](#), separately for each treatment by using the **CCI**.

The plasma concentration levels in the **CCI** are measured using a validated LC-MS / MS method. The procedure for validation and the acceptance limits are based on the requirements of the EMA Guideline (Guideline on bioanalytical method validation (EMEA / CHMP / EWP / 192217/2009 Rev. 1 Corr. 2 **), July 2011).

The statistical analysis will be carried out on a log scale for $AUC_{0-4\text{ h}}$ and C_{\max} -values, while t_{\max} and trough levels will be evaluated on a linear scale. Analyses of variance will be performed to compare the treatment groups.

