## 6 CHANGES TO STUDY PROTOCOL

The planned analysis will be performed according to the study protocol, its amendments and this statistical analysis plan. If there are contradictions between the study protocol or its amendments and this statistical analysis plan, the analysis will be performed according to this analysis plan. Any deviation from the planned analysis has to be described in the CSR.

The differences between study protocol and statistical analysis plan are summarized in the following table:

Change	Clinical Study Protocol (CSP)	In the Statistical Analysis Plan Will be changed to:
Wording in CSP	Major Protocol Deviation Minor Protocol Deviation	Important Protocol Deviation Non-Important Protocol Deviation

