## 8.4 Secondary Endpoints

- IMP tolerability and safety during the first 12 weeks of treatment (using the outcomes listed in Section 8.3)
- CsA PK, using the following parameters:
  - Week 0, at pre-dose; directly after end of inhalation; 15, 30, and 45 minutes, and 1, 1.5, 2, and 4 hours after end of inhalation: Cmax, tmax, AUC0-4h
- Whole blood trough levels parameter (Cyclosporine A Concentration) at week 2, 4, 8, and 12

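### SAP 14.2 limits the formal PK comparison to AUC0-4h and Cmax from the first dose; trough levels, the only repeated-dose PK data, lose the between-arm interval that the protocol wording covers, and SAP section 6 does not declare it

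*SAP*

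**What the plan says.** **Protocol.** Section 14.2.5 puts AUC0-4h and Cmax on a log scale, then continues: tmax "and trough levels will be evaluated on a linear scale. Analyses of variance will be performed to compare the treatment groups". The Statistical Considerations part of the synopsis has the same structure: a multiplicative model for AUC0-4h and Cmax, and for tmax and trough levels an "additive model. Analyses of variance will be performed to compare the treatment groups". In neither place is the analysis of variance limited to some of the four measures.

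**SAP.** Section 14.2 repeats the scale sentence, so tmax "and trough levels will be evaluated on a linear scale". The next step is narrower: "Analyses of variance will be performed to compare the treatment groups with regards to" AUC0-4h and Cmax, with 95% confidence intervals for the between-group differences. For trough levels the section keeps summary statistics: "Whole blood trough level parameter (Cyclosporine A Concentration) at Weeks 2, 4, 8, and 12, separately for each treatment group". A general rule in SAP 9.1 adds: "For all measures analyzed, tabulations comparing the treatment groups will be prepared".

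**Timing.** SAP 8.4 places the sampling for Cmax, tmax and AUC0-4h at "Week 0, at pre-dose; directly after end of inhalation" and up to 4 hours afterwards. The SAP schedule of activities (Table 1, note 5) makes every later PK sample a trough.

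**Declared changes.** SAP section 6 says: "The differences between study protocol and statistical analysis plan are summarized in the following table". The table has one row, which renames major and minor deviations as important and non-important.

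**The concern.** CsA PK is a secondary endpoint (SAP 8.4), and the secondary objective in SAP section 7 is comparative: PK of two dose levels against placebo. After the first dose, of up to 12 x 7 x 2 = 168, trough levels are the only PK information. The SAP gives an interval for the arm difference at the first dose and none for any time after it.

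This matters for the question the trial opens. Protocol 6.1.5 reports negligible serum levels and no accumulation in prior L-CsA studies, which section 6.1.4 shows were in lung-transplant recipients. The same section 6.1.5 says that this is the first PK evaluation after allogeneic HSCT. Only the troughs can speak to accumulation here.

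The retained linear-scale sentence for tmax and trough now has no comparison attached. That looks more like an oversight than a decision, although the documents do not say which it is.

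**Working it through.** There is no figure in the plan to reproduce. The sample size of 24 (3 x 8) is a feasibility figure (SAP 9.2), and no SD is given for any PK measure. The check is a comparison of texts, then a count, then an illustration of precision.

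**1. Scope, side by side**

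| Measure | Time | Protocol 14.2.5 and synopsis | SAP 14.2 |
|---|---|---|---|
| AUC0-4h | Week 0 | log scale, ANOVA | log scale, ANOVA with 95% CI |
| Cmax | Week 0 | log scale, ANOVA | log scale, ANOVA with 95% CI |
| tmax | Week 0 | linear scale, ANOVA by unrestricted wording | linear scale, by-arm summary only |
| Trough | Weeks 2, 4, 8, 12 | linear scale, ANOVA by unrestricted wording | linear scale, by-arm summary only |

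**2. Count.** Treat each trough visit as a separate outcome-timepoint. This is a counting convention; the protocol does not say whether the visits are analysed singly or together.

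- Protocol: 3 at Week 0 + 4 troughs = 7.
- SAP: 2 at Week 0 + 0 troughs = 2.
- Under repeated dosing: 4 against 0.

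At most 24 x 4 = 96 trough samples are left without a formal comparison.

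**3. Precision of a restored per-visit contrast.** With n per arm, three arms and a pooled variance, the 95% half-width in SD units is t(0.975, 3n - 3) x sqrt(2/n).

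- n = 8: 2.080 x 0.500 = 1.04 SD (21 df)
- n = 7: 2.101 x 0.535 = 1.12 SD (18 df)
- n = 6: 2.131 x 0.577 = 1.23 SD (15 df)

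The values n = 7 and n = 6 are assumed, to show the effect of missing samples.

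**4. Averaging over visits.** With k visits and a common between-visit correlation r, the half-width is multiplied by sqrt((1 + (k - 1)r)/k). The values of r are assumed.

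| | r = 0.3 | r = 0.5 | r = 0.7 |
|---|---|---|---|
| k = 4 | 0.72 SD | 0.82 SD | 0.92 SD |
| k = 2 | 0.84 SD | 0.90 SD | 0.96 SD |

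The k = 4 row is a best case. Troughs are drawn only at on-site visits (Protocol 12.1.6.3), and Visits 3 and 4 may be remote because of COVID-19 (Protocol 13.2.7). Visits 2 and 5 are the only trough visits that must be on site (synopsis), so k = 2 is the case in which both middle samples are lost.

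**5. Is placebo a zero reference?** Protocol 10.1.2 permits systemic CsA at the investigator's discretion, and no exclusion criterion in section 9.2 bars it. Section 6.1.5 says that exposure from L-CsA is much lower than from oral or IV therapeutic doses. Placebo troughs can therefore be well above zero, and with 8 per arm a few systemic users could dominate an arm mean on the linear scale. The data to deal with this are already collected: a Visit 1 pre-dose CsA sample (Protocol 12.1.6.2), recorded concomitant medication (10.1), and the immunosuppressant flag in SAP 15.3.

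**The case against.** **The SAP may narrow the analysis.** This stands. Protocol section 14 makes the final SAP the analysis of record and sends the reasons for discrepancies to the CSR; SAP section 6 also gives the SAP precedence. A reader might infer that the SAP breaches the protocol, and the documents do not support that. What remains is that section 6 presents itself as the summary of differences and omits this one.

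**Repeated-dose data are still shown by arm.** This stands too. A reader might infer that the SAP leaves no repeated-dose PK comparison of any kind. In fact SAP 14.2 keeps N, mean, SD, geometric mean and CV, median and range per arm at each trough visit, and SAP 9.1 calls for comparative tabulations. A simple per-visit interval could be computed from these. They do not allow one that accounts for pre-dose level or systemic CsA use.

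**The protocol does not name trough or tmax in its ANOVA sentence.** True. Their inclusion rests on unrestricted wording directly after a sentence covering all four measures, which is the natural reading. The protocol sets out no arm pairs, visits or intervals for PK, so no particular number of planned pairwise contrasts can be said to have been dropped.

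**The trial is purely descriptive and no decision depends on a trough ANOVA.** True, and it limits the weight of the point. But the SAP plans intervals for AUC0-4h, Cmax, spirometry and SF-36 under the same concept, so a trough interval would be no less descriptive.

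**A raw active-versus-placebo difference could mislead.** This also stands. One might assume that placebo troughs are near zero, but permitted systemic CsA contradicts that. It is a reason to specify the comparison with care, not to leave it out.

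**Conclusion.** The point holds as an undeclared narrowing. SAP 14.2 confines the formal PK comparison and its intervals to two first-dose measures, where the protocol wording covers seven outcome-timepoints, four of them under repeated dosing. The loss is the modelled between-arm estimate and its interval for trough levels. The by-arm summaries remain, and the change is within the SAP's authority.

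It should be corrected because the secondary PK objective is comparative and troughs are its only evidence after the first dose. If the comparison is added later in the CSR, SAP section 5 requires it to be identified as not described in the SAP. The primary tolerability and safety assessment is unaffected.

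The count assumes that each trough visit is counted separately and that the protocol's unrestricted ANOVA sentence covers all four measures. The precision figures are illustrative. The 1.04 SD assumes 8 evaluable patients per arm and a common variance, and will change with arm-specific variances. The averaged figures also assume the between-visit correlation.

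**What to change.** - **Trough levels, SAP 14.2.** Restore a between-arm comparison for 10 mg v placebo, 5 mg v placebo and 10 mg v 5 mg, with 95% confidence intervals at Weeks 2, 4, 8 and 12. An average over the available visits is optional. Allow unequal variances between arms.
- **Systemic CsA.** Adjust for the Visit 1 pre-dose CsA level and/or concomitant systemic CsA use, or repeat the comparison without systemic CsA users. Use recorded at baseline is the cleaner covariate. Use that starts later is a post-randomization event, so an analysis that adjusts for it or excludes those patients is best labelled a sensitivity analysis.
- **tmax.** Either list and justify the removal in section 6, or compare 10 mg v 5 mg only, since placebo delivers no CsA and its tmax has no drug-related meaning.
- **Section 6.** Add a row for any part of the protocol's PK comparison that stays out, with the reason. If the sponsor keeps trough levels descriptive, this row would cure the inconsistency but would leave the comparative PK objective without an interval under repeated dosing.

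The cost is SAP wording and one or two tables from data already collected. The downside is a few more unadjusted, wide intervals, to be read as estimates.
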